2.6.2 Statistical hypothesis, model, and method of analysis

The number and percentage of responders will be presented by cohort group (and overall) and time point (where appropriate). The 2-sided 95% CI for the proportion of responders will be calculated using an exact method ([Clopper and Pearson, 1934](#)). Participants achieving immune conversion will be summarized in a similar fashion.

2.6.3 Handling of intercurrent events

NRI approach will be applied to missing antibody assay regardless of intercurrent events.

2.6.4 Handling of missing values not related to intercurrent event

NRI approach will be applied to missing antibody assay.

2.6.5 Sensitivity analyses

There are no sensitivity analyses of secondary endpoints planned for this study.

2.6.6 Supplementary analyses

A supplemental analysis of each secondary endpoint will be performed using an observed case approach (completers) by using valid assessments of antibody assay without imputation of missing data.

In addition, analysis of secondary endpoints will be repeated using data from Cohort 6 participants and any participants in Cohorts 1 – 5 who received an mRNA booster during the study. Missing antibody assay will be handled according to the NRI approach.

The number and percentage of responders will be presented by cohort group and overall. The 2-sided 95% CI for the proportion of responders will be calculated using an exact method ([Clopper and Pearson, 1934](#)). Participants achieving immune conversion will be summarized in a similar fashion.

2.7 Safety analyses

2.7.1 Adverse events (AEs)

Adverse events (AEs) will be coded using MedDRA terminology. The MedDRA version used for reporting the study will be indicated in a footnote on relevant outputs.

For reporting purposes, summary tables for AEs will summarize only on-study events, which started or worsened on or after the date of Visit 1 (Screening).

The number and percentage of participants with on-study AEs will be summarized in the following ways:

- by cohort group, primary SOC and PT
- by cohort group, primary SOC, PT and maximum severity
- by cohort group and PT

Separate summaries will be provided for MS treatment-related AEs (MS treatment includes ofatumumab, interferon and glatiramer acetate), serious adverse events (SAEs) and other significant AEs leading to discontinuation.

If a participant reported more than one AE with the same PT, the AE with the greatest severity/grade will be presented. A participant with multiple AEs within a primary SOC is only counted once towards the total of the primary SOC.

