### **12.5.1 Safety endpoints**

All listings and tables will be presented by cohort.

In particular, summary tables for adverse events (AEs) will summarize only on-treatment events, which started or worsened during the on-treatment period (treatment-emergent AEs).

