## **Adverse events**

All information obtained on adverse events will be displayed by cohort and participant.

The number (and percentage) of participants with treatment emergent adverse events will be summarized in the following ways:

[figure not shown]
- by cohort, primary system organ class and preferred term.
- by cohort, primary system organ class, preferred term and maximum severity.
- by cohort, preferred term in descending order

Separate summaries will be provided for study medication related adverse events, serious adverse events, and other significant adverse events leading to discontinuation.

In addition, a separate listing of death including on treatment and post treatment deaths will be provided.

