### **Clinical laboratory evaluations**

All laboratory data will be listed by cohort, participant, and visit/time and if normal ranges are available abnormalities will be flagged. Summary statistics will be provided by cohort. Shift tables using the low/normal/high/ (low and high) classification will be used to compare baseline to the worst on-treatment value.

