2.13 Interim analysis

For the purpose of early dissemination of results, an IA will be performed once Cohorts 2 and 4 in combination have ≥ 10 participants enrolled that have had their serum drawn ≥ 14 days after full course (2 doses) vaccination.

A second IA will be performed once Cohort 6 has ≥ 10 participants.

The third IA will be performed once Cohorts 2 – 5 have full enrollment with blood drawn ≥ 14 days after full course (2 doses) vaccination.

The following variables (including but not limited to) will be summarized for each IA mentioned above:

- Disposition
- Demographics

- Baseline characteristics
- Immune response-related variables
- AEs, SAEs and AEs leading to study discontinuation
- Deaths

Since there will be no hypothesis testing involved, statistical adjustment for the IA will not be made at the stage of final analyses.

3 Sample size calculation

The sample size of 20 participants per cohort is selected based on budget and need for early availability of results. This sample size of 20 participants will provide estimates of proportion of responders with margin of error (half-width of a 95% CI) of 20.1%, 19% and 17.5% corresponding to response rates of 70%, 75% and 80%, respectively. Adjusting for 10% drop-out, 22 participants will be enrolled in Cohort 1. In combination, 22 participants will be enrolled in Cohorts 2 and 4. In combination, 22 participants will be enrolled in Cohorts 3 and 5. In Cohort 6, 22 participants will be enrolled.

4 Change to protocol specified analyses

There are no changes to protocol specified analyses.

5 Appendix

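### The SAP's AE window and laboratory displays differ from the protocol without being declared, and its Cohort 1 AE tables do not separate the time before ofatumumab from the time on it

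*SAP*

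**What the plan says.** **AE window.** Protocol 12.5.1 says that "summary tables for adverse events (AEs) will summarize only on-treatment events, which started or worsened during the on-treatment period (treatment-emergent AEs". SAP 2.7.1 says that "summary tables for AEs will summarize only on-study events, which started or worsened on or after the date of Visit 1 (Screening".

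**Laboratory data.** Under clinical laboratory evaluations, Protocol 12.5.1 says "Shift tables using the low/normal/high/ (low and high) classification will be used", setting baseline against the worst value on treatment. SAP 2.7.3 plans only descriptive statistics of values and of changes from pre-vaccination.

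**Display.** Protocol 12.5.1 says "All listings and tables will be presented by cohort" and lays out the AE tables "by cohort, primary system organ class and preferred term". The opening of Protocol Section 12 instead asks for four groups: Cohort 1, Cohorts 2 and 4, Cohorts 3 and 5, and Cohort 6. SAP 2.1 and 2.7 use the four groups.

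**Related events.** The protocol plans a summary of AEs related to study medication. The SAP says "Separate summaries will be provided for MS treatment-related AEs", meaning ofatumumab, interferon and glatiramer acetate.

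**Declaration.** SAP Section 1 says the document will cover deviations from the planned protocol analyses and names protocol version 01 of 29 September 2021. SAP Section 4 says "There are no changes to protocol specified analyses". The protocol reviewed here is at Amendment 2.

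**The concern.** AEs and SAEs are a secondary endpoint. No hypothesis is tested, so the descriptive tables are the safety result; AE summaries also enter each interim analysis.

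Cohort 1 is the one cohort that starts its MS drug during the study, and it does so after both vaccine doses. A table that counts everything from Visit 1 puts screening events and reactions to two vaccine doses under the heading of an ofatumumab cohort. A reader of that table cannot tell which events came before any ofatumumab was given.

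The shift table is the protocol's only planned summary that sets each participant's baseline category against the worst later category. Without it, movement from normal to low immunoglobulin has to be pieced together from listings. If Section 4 records no changes, someone comparing the study report with the protocol has no explanation for either difference.

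**Working it through.** **Inputs for Cohort 1** (nominal schedule)

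| Input | Pfizer | Moderna | Source |
|---|---|---|---|
| Planned first vaccine dose (Visit 2, Study Day 1) | 1 | 1 | Protocol Tables 8-1, 8-2; SAP 2.1.1 |
| Planned second vaccine dose (Visit 3) | 22 | 29 | Protocol Tables 8-1, 8-2 |
| Second dose to first ofatumumab dose | 14 days | 14 days | Protocol Section 3 |
| First ofatumumab dose | Day 36 | Day 43 | Protocol Table 6-3 |
| End-of-study visit | Day 382 | Day 389 | Protocol Tables 8-1, 8-2 |
| Screening length *s* | 0 to 7 days | 0 to 7 days | Protocol Section 3 |

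**1. Reproduce the plan's own figure.** 22 + 14 = 36 and 29 + 14 = 43. Both match Table 6-3.

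**2. Days in the SAP window before ofatumumab** = *s* + (first ofatumumab day − 1).
- Pfizer: 0 + 35 = 35, up to 7 + 35 = 42.
- Moderna: 0 + 42 = 42, up to 7 + 42 = 49.

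**3. Share of the time to end of study** = days before ofatumumab / (*s* + end-of-study day).
- Pfizer: 35/382 = 9.2%, up to 42/389 = 10.8%.
- Moderna: 42/389 = 10.8%, up to 49/396 = 12.4%.

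The denominator stops at the end-of-study visit because AEs at the later safety contact are marked for source documentation only.

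**4. Time from the first ofatumumab dose to end of study:** 382 − 36 + 1 = 347 days and 389 − 43 + 1 = 347 days.

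**5. How much of the mixing comes from the SAP?** That depends on when the protocol's undefined on-treatment period begins.

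| On-treatment begins at | Pre-ofatumumab days in the protocol's table | Days the SAP window adds |
|---|---|---|
| First vaccine dose, Day 1 | 35 (Pfizer), 42 (Moderna) | Screening only, 0 to 7 |
| First ofatumumab dose | None | 35 to 42 (Pfizer), 42 to 49 (Moderna) |

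Under either reading the SAP's Cohort 1 table covers the same 35 to 49 days before ofatumumab without a split. Cohorts 2 to 6 are already on their MS drug at screening, so they have no such stretch.

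**6. Laboratory data.** The shift table appears in the protocol and nowhere in the SAP's safety section. The SAP's pre-vaccination baseline applies only to Cohorts 1 to 3 (SAP 2.1.1), so for Cohorts 4 to 6 the SAP provides neither a shift from baseline nor a change from it.

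**The case against.** Several replies carry weight.

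- **Grouping.** A reader might infer that the SAP introduced the pooling of Cohorts 2 with 4 and 3 with 5. The documents do not support that. The opening of Protocol Section 12 prescribes those groups and the sample size section uses them. The protocol contradicts itself, and the SAP follows one of its two statements.
- **Cause of the mixing.** A reader might infer that the SAP's window alone creates the Cohort 1 problem. The protocol has cues for treatment starting at Day 1: the Treatment period in Table 8-1 begins at Visit 2, the treatment durations of 382 and 389 days in Protocol 4.2 equal the end-of-study day, and Table 6-1 lists the vaccine. On that reading the protocol's own table would mix the same events, and the SAP adds screening only.
- **Hidden low IgG.** It is tempting to say that mean changes conceal participants who fall to low values. SAP 2.1 reports minimum and 25th percentile and lists all data. Protocol 8.5.2 withdraws participants with IgG below 400 mg/dl, so they should also appear in the discontinuation listing. A display has been lost, but the data are not hidden.
- **Vaccine-related events.** A vaccine-related AE summary looks like an obvious omission. Protocol 10.1.1 asks only for relationship to the study treatment, and assessment by treatment component is stated only for SAEs (Protocol 10.1.3). The documents do not show that vaccine causality was recorded for non-serious AEs.
- **Section 4.** It refers to protocol version 01, whose safety text cannot be compared here.

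These replies narrow the point but leave its core standing. The AE window and the shift tables differ from the current protocol. The summary of MS-treatment-related AEs separates Cohort 1 events by judged causality, not by time. The listings help little, because SAP 2.1.1 counts onset day from Visit 1 and not from a dose.

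**Conclusion.** The point holds in limited form. Against the protocol at Amendment 2, the SAP changes the AE window and drops the shift tables, and Section 4 records neither. Whether that statement was accurate for version 01 cannot be determined.

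The practical consequence falls on Cohort 1: 35 to 42 days (Pfizer) or 42 to 49 days (Moderna) before ofatumumab are reported together with 347 days from its first dose. The share of time is modest, 9.2% to 12.4%, but it holds both vaccine doses and the 14 days after the second. These figures assume the nominal visit days. Protocol Section 8 ties Visit 4 to the actual date of the second vaccine dose, so individual intervals will vary.

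The primary endpoint is untouched and no error rate is involved. The correction is worth making before the safety tables are run. The documents do not support going further and setting new onset rules for Cohorts 2 to 6.

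**What to change.** 1. **Define the AE reporting period for each cohort** in the SAP, and align the protocol's on-treatment wording with it.
2. **Split the Cohort 1 AE tables** into events before the first ofatumumab dose and events starting or worsening from that dose. Use as denominator for the second part the participants who received at least one dose, and state the length of each period. Add a rule for onset on the dosing day and for partial dates: SAP 5.1.2 imputes AE start dates relative to Visit 1 only and could put an event on the wrong side of the split.
3. **Restore the baseline-to-worst shift tables**, at least for IgG and IgM, and name the baseline for Cohorts 4 to 6. Keep a missing-baseline row, because participants with local results from the past 6 months need no central screening sample and those results are documented in source (footnote to Protocol Tables 8-1 to 8-6).
4. **Reconcile the two protocol statements on display**, the four groups at the opening of Section 12 and by cohort in 12.5.1, for the safety tables.
5. **List what still differs in SAP Section 4**, and name the protocol version it is checked against.

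Add a vaccine-related summary only if vaccine causality was recorded.

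The cost is a few more tables. AE dates, Cohort 1 dosing dates and post-vaccination immunoglobulins are already collected. With 22 participants planned in Cohort 1, cell counts will be small, and smaller still if Cohorts 2 to 5 are shown individually.

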## 5 Study Population

The study population will consist of male and female participants,  $\geq 18$  years of age to 55 years of age inclusive, with a diagnosis of relapsing MS.

The study aims to enroll up to 88 participants at up to 30 centers in the United States. Since a 25% screen failure rate is expected, approximately 117 participants will be screened. 22 participants will be enrolled in Cohort 1. In combination, 22 participants will be enrolled in Cohorts 2 and 4. In combination, 22 patients will be enrolled in Cohorts 3 and 5. In Cohort 6, 22 participants will be enrolled.

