5. Completed a full course (two doses) of a COVID-19 mRNA vaccine at least  $\geq 4$  weeks after start of commercially prescribed ofatumumab for the treatment of RMS
6. Currently on commercially prescribed ofatumumab for  $\geq 4$  weeks for the treatment of RMS
7. Received two dose mRNA COVID-19 vaccine (Pfizer or Moderna vaccine)  $\geq 2$  weeks ago
8. Pre-ofatumumab serologies with Hepatitis B testing not indicative of active or latent infection
9. Total serum immunoglobulin IgG  $\geq 400$  mg/dl at Screening

Patients eligible for inclusion in Cohort 5 of this study must meet **all** of the following criteria:

1. Signed informed consent must be obtained prior to participation in the study
2. Age 18-55 years old at Screening
3. Diagnosis of relapsing MS by 2017 revised McDonald criteria
4. Must be willing to comply with the study schedule
5. Currently on commercially prescribed interferon or glatiramer acetate for  $\geq 4$  weeks for the treatment of RMS
6. Completed a full course (two doses) of a COVID-19 mRNA vaccine after start of glatiramer acetate or interferon
7. Received two dose mRNA COVID-19 vaccine (Pfizer or Moderna vaccine)  $\geq 2$  weeks ago
8. If the patient has received the mRNA booster, then the mRNA booster should be  $\geq 2$  weeks prior to enrollment.
9. Total serum immunoglobulin IgG  $\geq 400$  mg/dl at Screening

Patients eligible for inclusion in Cohort 6 of this study must meet **all** of the following criteria:

1. Signed informed consent must be obtained prior to participation in the study
2. Age 18-55 years old at Screening
3. Diagnosis of relapsing MS by 2017 revised McDonald criteria
4. Must be willing to comply with the study schedule
5. Currently on commercially prescribed ofatumumab for  $\geq 4$  weeks for the treatment of RMS

6. Completed a full course (two doses) of a COVID-19 mRNA vaccine at least  $\geq$  4 weeks after start of commercially prescribed ofatumumab for the treatment of RMS
7. Received two dose mRNA COVID-19 vaccine (Pfizer or Moderna vaccine)  $\geq$  2 weeks ago
8. Pre-ofatumumab serologies with Hepatitis B testing not indicative of active or latent infection
9. Total serum immunoglobulin IgG  $\geq$  400 mg/dl at Screening
10. Has received an mRNA booster  $\geq$  2 weeks prior to enrollment

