### **Special guidance regarding the scheduling of visits for Cohorts 1, 2 and 3**

- The study site will need to perform Vaccine Status Check-ins (make remote contact with participant) to confirm when the 1st and 2nd COVID-19 vaccinations are scheduled in order to schedule Visit 4.
- The date of the 2nd COVID-19 vaccine dose will determine the date of Visit 4 and all other remaining study visits.
- Visits 2 and 3 should always occur prior to administration of the mRNA vaccine.
- The Visit 4 lab samples should be collected 14 days after a participant has received their 2nd COVID-19 vaccine dose.

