**Table 8-3 Assessment schedule for Cohorts 2 and 3 (Pfizer vaccine)**

Period	Screening	Treatment						Follow-up	
Visit Name	Visit 1 Screening	Visit 2	Visit 3	Visit 4	Visit 5	Visit 6	Visit 7/End of Study (EOS)	Visit 8 / Safety	Unscheduled
Day/Week/Month	Day -7	Day 1	Day 22	Day 36	Day 202	Day 292	Day 382	Day 412	
Visit Window				+3d	+/-3d	+/-3d	+/-3d	+/-3d	
Obtain informed consent	X								
Inclusion/exclusion criteria	X								
Demography	X								
Relevant medical history/current medical history	X								
Non-drug therapies and procedures	X	X	X	X	X	X	X	S	X
Prior/Concomitant Medications	X	X	X	X	X	X	X	S	X
MS Relapse	X	X	X	X	X	X	X	S	X
Serum Pregnancy Test 	S						S		

Period	Screening	Treatment						Follow-up	
Visit Name	Visit 1 Screening	Visit 2	Visit 3	Visit 4	Visit 5	Visit 6	Visit 7/End of Study (EOS)	Visit 8 / Safety	Unscheduled
Day/Week/Month	Day -7	Day 1	Day 22	Day 36	Day 202	Day 292	Day 382	Day 412	
Visit Window				+3d	+/-3d	+/-3d	+/-3d	+/-3d	
Hepatitis B virus (HBV) (Cohort 2 only) 	X								
SARS CoV2 qualitative antibody		X	X	X	X	X	X		
Serum Immunoglobulin 	X				X		X		
CD 19+ B cells (Cohort 2 only)	X	X	X	X	X	X	X		
Biobanked serum sample 	X			X					
Biobanked whole blood sample 	X			X					
Vaccine Administration Form		X	X						
IRT Transaction	X	X	X	X	X	X	X		
Drug Accountability		S	S	S	S	S	S		
Adverse Events / Serious Adverse Events	X	X	X	X	X	X	X	S	X
Subject disposition	X						X	S	

X = assessment to be recorded in the clinical database or received electronically from a vendor

S = assessment to be recorded in the source documentation only

 Serum pregnancy should be performed locally for all sites except those unable to use a local lab. Sites unable to perform locally should send sample to the central lab.

 Participants with lab results within the past 6 months prior to screening will not require labs drawn at screening visit. Local labs should be documented in the source. Participants without lab results from the past 6 months prior to screening will require central labs drawn at the screening visit to be entered into the clinical database.

 Sample will be bio-banked for yet to be identified analyses.

 Vaccine check-ins (remote contacts) by site staff to confirm participant has received the COVID-19 vaccine and to collect any AEs/SAEs.

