## **10 Safety monitoring, reporting and committees**

### **10.1 Definition of adverse events and reporting requirements**

#### **10.1.1 Adverse events**

An adverse event (AE) is any untoward medical occurrence (e.g. any unfavorable and unintended sign [including abnormal laboratory findings], symptom or disease) in a clinical investigation participant after providing written informed consent for participation in the study. Therefore, an AE may or may not be temporally or causally associated with the use of a medicinal (investigational) product.

The investigator has the responsibility for managing the safety of individual participant and identifying adverse events.

Novartis qualified medical personnel will be readily available to advise on trial related medical questions or problems.

The occurrence of adverse events must be sought by non-directive questioning of the participant at each visit during the study. Adverse events also may be detected when they are volunteered by the participant during or between visits or through physical examination findings, laboratory test findings, or other assessments.

Adverse events must be recorded under the signs, symptoms, or diagnosis associated with them, accompanied by the following information (as far as possible) (if the event is serious refer to [Section 10.1.2](#)):

1. The Common Toxicity Criteria (CTC) AE grade (1-5)
  - 1 = mild: usually transient in nature and generally not interfering with normal activities
  - 2 = moderate: sufficiently discomforting to interfere with normal activities
  - 3 = severe: prevents normal activities
  - 4 = life threatening
  - 5 = death
2. Its relationship to the study treatment. If the event is due to lack of efficacy or progression of underlying illness (i.e. progression of the study indication) the assessment of causality will usually be 'Not suspected.' The rationale for this guidance is that the symptoms of a lack of efficacy or progression of underlying illness are not caused by the trial drug, they happen in spite of its administration and/or both lack of efficacy and progression of underlying disease can only be evaluated meaningfully by an analysis of cohorts, not on a single participant
3. Its duration (start and end dates or ongoing) and the outcome must be reported
4. Whether it constitutes a SAE (see [Section 10.1.2](#) for definition of SAE) and which seriousness criteria have been met
5. Action taken regarding with study treatment.

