2.1 Data analysis general information

The statistical analysis outlined in this SAP will be performed by [REDACTED], a Novartis-designated Contract Research Organization (CRO), using SAS® version 9.4 or higher.

For continuous variables, descriptive statistics will include number of participants (n), mean, standard deviation, minimum, maximum, median and 25th and 75th percentiles. For categorical variables, frequency counts and percentages will be reported. Where appropriate, 2-sided 95% confidence intervals (CIs) for point estimates of the mean or proportion will be provided.

Unless otherwise stated, all data summaries will be presented by **cohort group** (see below) and on all participants in the respective analysis set.

- Cohort 1
- Cohorts 2 and 4 combined
- Cohorts 3 and 5 combined
- Cohort 6

All data will be listed appropriately.

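### Pooled adverse-event percentages for Cohorts 2+4 and 3+5 depend on the recruitment mix as well as on any drug effect, because the two-dose vaccination period is observed only in the vaccine-naive cohorts

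*SAP*

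**What the plan says.** **AE window.** SAP 2.7.1: "summary tables for AEs will summarize only on-study events, which started or worsened on or after the date of Visit 1 (Screening"). The same rule applies to all six cohorts and takes no account of the vaccine date. Protocol 10.1.1 likewise starts AEs at consent, defining them as occurrences "in a clinical investigation participant after providing written informed consent for participation in the study".

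**Vaccination in Cohorts 2 and 3.** The protocol's scheduling guidance says "Visits 2 and 3 should always occur prior to administration of the mRNA vaccine". A footnote to Table 8-3 adds active questioning: "Vaccine check-ins (remote contacts) by site staff to confirm participant has received the COVID-19 vaccine and to collect any AEs/SAEs".

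**Vaccination in Cohorts 4 and 5.** Entry under Protocol 5.1 requires "Received two dose mRNA COVID-19 vaccine (Pfizer or Moderna vaccine") at least 2 weeks earlier. Tables 8-5 and 8-6 contain no vaccine check-ins.

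**Table columns.** SAP 2.1: "Unless otherwise stated, all data summaries will be presented by" cohort group, with 2 and 4 combined and 3 and 5 combined. SAP 2.7.1 applies this to AEs, for example "by cohort group, primary SOC and PT". SAP 2.2.1 plans no subgroup analysis.

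**Sample size.** Protocol 5: "In combination, 22 participants will be enrolled in Cohorts 2 and 4". Cohorts 3 and 5 have the same arrangement. Neither split is fixed.

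**Conflict.** Protocol 12.5.1 has safety tables presented by cohort and limited to treatment-emergent events. The opening of Protocol 12 has all summaries use the four pooled groups. The SAP uses the pooled groups and an on-study window, and SAP section 4 declares no change from the protocol.

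**The concern.** AEs are a secondary objective, the vaccine is the treatment of interest, and Protocol 4.1 calls Cohorts 3 and 5 a comparator. The 2+4 and 3+5 columns are therefore likely to be read side by side. Each column mixes participants who were followed through a two-dose course with participants whose course ended before follow-up began. Reactions to those doses can be counted in the first kind of participant and not in the second.

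Nothing in the design makes the mix alike in the two columns. There is no randomization, eligibility determines the cohort, and Amendment 1 added the vaccinated cohorts because vaccination in the US was slowing. AE summaries are also produced at each of the three interim analyses for early dissemination. The first of these is triggered by as few as 10 participants in Cohorts 2 and 4 together, where the mix could be extreme.

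**Working it through.** The documents give no figure for AEs. Their precision calculation (Protocol 12.8.1) reproduces as 1.96 × √(p(1−p)/20) = 20.08%, 18.98% and 17.53% at 70%, 75% and 80%, against the stated 20.1%, 19% and 17.5%. It does not bear on this point.

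**Inputs from the documents**
- Window opens at Visit 1 (Day −7) in every cohort.
- Cohorts 2 and 3: doses follow Visit 2 (Day 1) and Visit 3 (Day 22 Pfizer, Day 29 Moderna). Both fall inside the window.
- Cohorts 4 and 5: both doses precede entry. Both fall outside the window.
- Each pooled group has 22 participants, of whom k are vaccine-naive. Any k from 0 to 22 is allowed.

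**Assumed inputs (not in the documents)**
- v: probability of an AE in the two-dose period.
- b: probability of an AE at any other time, independent of the first.
- The values of k. No booster reactions.

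**Step 1: vaccine reactions only, no drug effect.** Pooled % = v × k/22.

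| v | k = 2 | k = 10 | Gap (points) |
|---|---|---|---|
| 30% | 2.7% | 13.6% | 10.9 |
| 50% | 4.5% | 22.7% | 18.2 |
| 70% | 6.4% | 31.8% | 25.5 |

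With k = 11 in both groups and v = 50%, both columns show 25.0% and there is no gap.

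**Step 2: any AE, no drug effect.** Pooled % = b + (k/22) × v × (1 − b). With b = v = 50%:

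| k | 0 | 5 | 11 | 17 | 22 |
|---|---|---|---|---|---|
| Pooled % | 50.0 | 55.7 | 62.5 | 69.3 | 75.0 |

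Mixes of 17/22 and 5/22 give a gap of (12/22) × 0.5 × 0.5 = 13.6 points with no drug effect. Over b = 30–70% and v = 20–80%, the gap for the same mixes runs from (12/22) × 0.2 × 0.3 = 3.3 to (12/22) × 0.8 × 0.7 = 30.5 points.

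**Step 3: a real difference.** Take b = 60% on ofatumumab, b = 40% on the comparator and v = 50% (gaps taken before rounding):
- 5/22 naive on ofatumumab and 17/22 on the comparator: 64.5% and 63.2%, gap 1.4 points.
- 17/22 and 5/22: 75.5% and 46.8%, gap 28.6 points.
- Equal mixes of 5, 11 or 17: gaps of 17.7, 15.0 and 12.3 points.

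The mix can therefore hide a difference as well as create one.

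**Step 4: individual cohorts.** With b = v = 50% and no drug effect, Cohorts 2 and 3 each show 1 − 0.5 × 0.5 = 75%, and Cohorts 4 and 5 each show 50%, whatever the split. The dependence on k disappears.

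**The case against.** A reader might infer that the pooled percentages reflect recruitment instead of the drug. The documents do not support that. The percentages carry both, and a false gap between the columns needs unequal mixes, which the plan permits but does not imply. That limit stands.

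The size rests on assumption. The documents give neither the splits nor the reaction rates, and the numbers are small: an expected 1 of 22 and 5 of 22 have exact 95% intervals of 0.1–22.8% and 7.8–45.4%. Step 1 also gives Cohorts 4 and 5 no vaccine reactions at all. Protocol 12.5 allows boosters during the trial, and reactions to those would fall inside the window, so the true gap could be smaller. Both reservations stand.

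There is some protection already. The separate table of MS-treatment-related AEs should leave out most vaccine reactions, data are listed by participant, and no hypothesis is tested. None of this corrects the main AE tables.

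It could be said that the word cohort in Protocol 12.5.1 loosely means the pooled groups of Protocol 12. That is possible, but the text does not say so, and the SAP itself separates the two terms: section 2.4.1 lists compliance by individual cohort.

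Visit frequency also differs between cohorts. It is a side issue here: Cohort 1, with the densest schedule, has its own column, and counts of scheduled visits omit the remote contacts at which AEs are also collected.

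**Conclusion.** The point holds in a limited form. It follows from the documents alone that the two-dose period lies inside the AE window for Cohorts 2 and 3 and before it for Cohorts 4 and 5, that these are pooled, and that the splits are open. The pooled 2+4 and 3+5 AE percentages therefore depend on the recruitment mix as well as on any drug effect.

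The size is illustrative. With a 50% reaction rate, 2/22 versus 10/22 vaccine-naive, no drug effect and no booster reactions, the columns read 4.5% and 22.7%. Equal mixes with no drug effect give no gap. The analyses are descriptive, so no error rate is affected, and the primary endpoint is untouched.

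Separately, Protocol 12, Protocol 12.5.1, SAP 2.7.1 and SAP section 4 do not agree and need reconciling in any case. This is a cheap improvement, not a flaw that threatens the study's main result.

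**What to change.** 1. In SAP 2.7.1, present the AE tables by individual cohort, as Protocol 12.5.1 states.
2. Keep the pooled whole-study columns only alongside, with a footnote that the two-dose vaccination period is observed in Cohorts 1–3 only.
3. Make any comparison of ofatumumab with interferon or glatiramer acetate within vaccination status: Cohort 2 with 3, and Cohort 4 with 5. These remain non-randomized and descriptive, and Cohort 5 may include participants boosted before entry while Cohort 4 does not.
4. Reconcile the opening of Protocol 12, Protocol 12.5.1 and SAP 2.7.1 on columns and on the on-treatment versus on-study window, and record the outcome in SAP section 4.
5. Optionally, add a table of AEs from first vaccine dose to Visit 4 for Cohorts 1, 2 and 3 separately. It needs a rule for a missing Visit 4 and a check on partial onset dates, since SAP 5.1.2 can set these to Visit 1, before vaccination.

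A period split that still pools the cohorts after the primary time point would not be enough. To the end-of-study visit, that period lasts 382 − 36 = 346 days in Cohorts 2–3 and 382 − 1 = 381 in Cohorts 4–5 on the Pfizer schedule (389 − 43 = 346 and 389 − 1 = 388 on Moderna). Events before the first dose, or before Visit 2 in Cohorts 4–6, would fall in no table.

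Steps 1 to 4 cost extra output columns and some SAP wording, with no new data or visits. The downside is smaller counts per column; a cohort that recruits only a few participants will support little beyond a listing.
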